6. STUDY DESIGN

This study is a multi-center non-randomized prospective observational post-marketing cohort study. The cohort of patients will be followed up for a minimum of 5 years after the treatment.

The study aimed to test the EVAR with the “prototype” device in mismatched renal arteries AAA.

Inclusion/exclusion criteria were reported above.

7. METHODS

Setting

Patients affected by AAA with an inter-renal distance $\geq 10\text{mm}$ and eligible for EVAR within standard TReO (Terumo Aortic) IFU will be prospectively enrolled at the Unit of Vascular Surgery of the Ospedale Civile di Baggiovara (Azienda Ospedaliero-Universitaria di Modena) and in the participating centers. The Investigators (3 experts Vascular surgeons⁹) will screen the patients for inclusion. Once the patient's eligibility will be stated, informed consent will be collected and the study could take place.

Inclusion criteria:

- Patients affected by infrarenal AAA $\geq 50\text{mm}$
- Treated in election for non-symptomatic AAA
- Anatomy inside Treo (Terumo Aortic) instruction to use (IFU)
- Distance between renal arteries $\geq 10\text{mm}$ on aortic center-lumen-line
- Age ≥ 18
- Patient fit to plead
- Both sex
- Written informed consent
- Treated in the coordinator center or in one of the study's participating centers
- Minimum follow-up requested: 3-months, 12-18 months and 5-years CTA; clinical and DUS examination at 6- and 12- and 36-months after the intervention and yearly thereafter

Exclusion criteria:

- Patients with aortic pathologies different from AAA (aortic ulcers, dissection, pseudo-aneurysm etc)
- Treated in urgent/emergent setting for symptomatic or ruptured AAA
- AAA < 50mm
- Outside TREO (Terumo Aortic) IFU
- With an inter-renal distance measured of the center-lumen-line <10mm
- Age <18
- Unfit to plead
- Refused to sign the informed consent
- Treated outside the coordinator centers or in one of the study's participating center's
- Refusal to adhere to the requested follow-up

Device description

TREO (Terumo Aortic) was described in different papers.¹⁰⁰⁻¹¹ It is a tri-modular device composed of self-expanding nitinol Z-stents sutured to woven polyester graft fabric. The stent-graft has a proximal bare stent with each edge presenting barbs. The second row of barbs is placed at the external surface of the proximal edge of the fabric. The barbs are nitinol, caudally-directed, sealing adjuncts promoting a better fixation.

The Manufacturer allows customization of the standard design. The investigational endograft was ideated with a single renal scallop (10x10-mm and 15x10-mm, height and width,

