4. BACKGROUND

Endovascular aneurysm repair (EVAR) is currently the preferred choice to treat the abdominal aortic aneurysms (AAA) with a feasible anatomy^{1,2}. However, approximately 40-60% of AAA patients presented unfavorable characteristics for EVAR, mainly due to a “hostile neck anatomy”³⁻⁵. In “real-world” clinical practice, up to 44% of EVAR cases are performed outside Instruction For Use (IFU) for an adverse neck anatomy⁶. Short (<15-mm), angulated (>60°), and wide (>28-mm) aortic necks are the main features concurring to the proximal HNA⁶.

The recourse to standard EVAR is currently routine for patients who are not eligible for OR, with acceptable short- and mid-term outcomes, but the long-term durability of EVAR depends on maintaining proper sealing between the endograft and the aortic neck as well as the iliac arteries⁷. HNAs demonstrated worse results when compared to “favorable” ones in terms of technical success (94% vs. 98%) and type-Ia endoleak rate (10% vs. 2%).⁶ The issue linked to an unfavorable anatomy can be addressed with more complex techniques, but these are limited by high production costs and considerable complexity.⁸⁻⁹

TREO (Terumo Aortic, Inchinnan, Renfrewshire, UK; formerly Treovance, Bolton Medical, Sunrise, Fla) is a standard bifurcated, modular stent-graft that has shown compelling early- and mid-term results¹⁰⁻¹¹. It seems clear that several physicians are still looking for a feasible solution for HNA patients to keep the complexity of the procedure comparable to standard EVAR while yielding improved results.

Moreover, there is a lack of publications addressing the issue of mismatched take-off of the renal arteries (RAs). This morphology seems to influence the sealing length and could justify

the introduction of dedicated devices. A recent study from our group currently under review for publication demonstrated that 25% of patients eligible for EVAR presented with mismatched RAs and that a dedicated device could improve sealing significantly. The study group sealing zone's length increased by about 25% when applying a hypothetical prototype with a single 10x10mm (wide x high) renal scallop. The same approach could be applied to the sealing surface with similar results.

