5. STUDY AIM

BASIC RESEARCH

To evaluate the clinical effectiveness of EVAR with an “off-the-shelf” single-renal-scallop endograft (TREO, Terumo Aortic) in the treatment of AAA patients with mismatched renal arteries. These data will be used to evaluate the clinical advantages of the adoption of a dedicated device for this kind of patients. See the protocol below for methods.

CLINICAL STUDY

To assess the real-world, in-vivo, clinical effectiveness of the use of a single-renal scallop endograft to treat infrarenal AAA. The study population is subjects with infrarenal AAA eligible for EVAR, of both sexes, aged 18>years, and with mismatched renal arteries. The mismatch was defined by a distance between the takeoff of the two proper renal arteries \geq of 10mm. The study group is intended for patients receiving EVAR with the pre-mentioned dedicated custom-made endograft (from now called Prototype). The clinical intervention will be performed in the study participating centers and for our competence at the Unit of Vascular Surgery (Ospedale Civile di Baggiovara, Azienda Ospedaliero-Universitaria di Modena, [name]).

Expected results and risk/benefit considerations

The results will demonstrate whether the “Prototype” is effective for the treatment of AAA with mismatched RAs. The effectiveness will be evaluated in terms of technical and clinical

success. Other objectives are the evaluation of procedure-related adverse events and re-interventions, as well as operative details.

The use of fenestrated and branched endograft has already been demonstrated to be safe and feasible for the treatment of HNA AAA¹³⁻¹⁴. However, the complexity of the repair, the high costs, and the significant risk of renal and neurological injury limited the widespread of these techniques^{8,9, 15}. On the other hand, standard EVAR has been used in HNA AAA with acceptable results in short- and mid-term period¹¹⁻¹². The actual challenge is to improve the outcomes of patients with unfavorable anatomy for standard EVAR keeping the complexity as low as possible.

Literature evaluating the mismatch of renal arteries in AAA patients is lacking and a recent study carried out in our unit demonstrated that about one-third of these presented an infrarenal distance of more than 10mm. These particular anatomical characteristics seem to influence the length of sealing and justify the evaluation of a dedicated device.

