The benefits could be relevant for the patients in terms of reduction of procedure-related adverse events such as endoleaks and related re-interventions. Furthermore, the use of custom-made standardized devices could produce a significant reduction in costs for health care providers and in the future, it could be the base for an “off-the-shelf” endograft. Procedure-related complications were expected to be similar to standard EVAR and reduced in comparison with literature reporting adverse events in more complex techniques. To confirm this forecast all adverse events will be reported in our CRF and prospectively monitored. Moreover, complications directly imputable to device defects will be promptly communicated to the regulatory authority and managed following law dispositions.

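### The plan to confirm fewer complications than with more complex techniques compares different anatomies, which favours the prototype

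*Combined protocol and SAP*

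**What the plan says.** The eligibility list in section 7 (Methods) requires infrarenal AAA and "Anatomy inside Treo (Terumo Aortic) instruction to use (IFU", and it excludes anatomy "Outside TREO (Terumo Aortic) IFU". Every enrolled patient is therefore one for whom the unmodified TREO graft is already indicated.

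The expected results in section 5 (Study Aim) make a two-part forecast. Complications should resemble those of standard EVAR, and they should be "reduced in comparison with literature reporting adverse events in more complex techniques". The next sentence says that adverse events will be recorded in order to confirm the forecast. The secondary-endpoint text in section 7 also names the standard-EVAR literature as the reference for procedure time, fluoroscopy time and contrast dose.

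On anatomy, section 4 (Background) states: "Short (<15-mm), angulated (>60°), and wide (>28-mm) aortic necks are the main features concurring to the proximal HNA". It adds that "up to 44% of EVAR cases are performed outside Instruction For Use (IFU) for an adverse neck anatomy". It presents complex techniques as the answer to unfavourable anatomy, and section 5 describes fenestrated and branched grafts as treatment for hostile-neck AAA.

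**The concern.** The study has one arm and no performance goal, so any statement that the prototype does better or worse rests on an outside series. If that series treated harder anatomy, a lower complication rate with the prototype could come from the device, from the easier necks, or from both, and the data cannot separate them. Section 5 nevertheless describes the exercise as confirmation. The results are also meant to inform a future off-the-shelf device, so a favourable contrast produced by case mix could carry weight in that decision.

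**Working it through.** **Step 1. Anatomy on each side of the comparison.**

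| | Prototype cohort | Complex-technique literature |
|---|---|---|
| Aneurysm | Infrarenal (section 7) | Juxtarenal in the titles of references 9, 13 and 14 |
| Neck | Inside the standard TREO IFU (section 7) | Unfavourable or hostile (sections 4 and 5) |

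Only the titles of the references were available. The plan does not say which series it will use.

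**Step 2. Direction.** The only outcome rates in the documents are in the Background. For hostile versus favourable necks under EVAR they are 94% versus 98% for technical success and 10% versus 2% for type-Ia endoleak. Harder anatomy goes with worse results, so the mismatch favours the prototype.

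**Step 3. Size.** No complication rate for complex techniques is given, so the bias in the planned comparison cannot be calculated. The next two steps show only how strongly case mix can act at this sample size.

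**Step 4. Illustration with the Background rates.**

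Inputs: n = 50 (section 7, Sample size, set by expected recruitment and not by a calculation); type-Ia rates 2% and 10%. Assumption: a fraction f of enrolled necks is hostile. The IFU limits are not in the documents, so f is varied from 0 to 1. A device with no benefit then has rate p = 2% + 8f percentage points.

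P(X ≤ 1) = (1 − p)^50 + 50p(1 − p)^49

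At p = 10% this is 0.0052 + 0.0286 = 0.034, the one-sided exact p-value of 1 event in 50 against 10%. At p = 2% it is 0.364 + 0.372 = 0.736.

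| f | p | P(at most 1 event) | P(0 events) |
|---|---|---|---|
| 0 | 2% | 0.74 | 0.364 |
| 0.25 | 4% | 0.40 | 0.130 |
| 0.50 | 6% | 0.19 | 0.045 |
| 0.75 | 8% | 0.08 | 0.015 |
| 1 | 10% | 0.03 | 0.005 |

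The last column applies if the test is two-sided at 0.05. Then only 0 of 50 is significant (one-sided p = 0.005), because 0.034 exceeds 0.025.

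**Step 5. The standard-EVAR reference.** Suppose that a real-world series has the maximum 44% of cases outside IFU, and that these carry the hostile-neck rate (an assumption). Its type-Ia rate is 2% + 0.44 × 8 points = 5.5%, or 2.8 events per 50. A device with no benefit gives at most 2 events, and so looks numerically better, with probability 0.92, 0.68 or 0.42 at f = 0, 0.25 or 0.50. With no out-of-IFU cases the reference falls to 2% and this source of bias disappears.

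**The case against.** The strongest objection is that the aim already fits the enrolled patients. Section 5 defines the population as EVAR-eligible with mismatched renal arteries, and the Background gives this its own rationale, noting that "25% of patients eligible for EVAR presented with mismatched RAs". This is correct, and neither aim nor population needs to change. A reader might infer from the sentence "The actual challenge is to improve the outcomes of patients with unfavorable anatomy for standard EVAR keeping the complexity as low as possible" that the study will draw a conclusion about hostile necks. That sentence describes the field, and the stated conclusion concerns AAA with mismatched renal arteries.

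A reader might also take the 94% and 10% rates as the study's comparator and conclude that a device with no benefit is bound to look better. The documents do not support that. Those rates appear once, beside the favourable-neck rates, and are never made a benchmark; the primary endpoint has none. The figure of 0.74 also requires every enrolled neck to be favourable and a one-sided reading.

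The forecast's first half, similarity to standard EVAR, points to a more suitable reference. That stands, subject to Step 5. Nor are the neck measurements unused: anatomical features are listed as possible risk factors for adverse events. What is missing is a hostile/favourable classification and its use in interpreting results.

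None of this removes the second half of the forecast, which names complex techniques and promises confirmation.

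**Conclusion.** The concern holds for the comparison with complex techniques. As written, it confounds device with anatomy in the prototype's favour, and the study cannot confirm that part of the forecast. The direction rests on the documents' own association of complex techniques with hostile or juxtarenal anatomy and on their worse EVAR results in hostile necks. The size is unknown. The standard-EVAR reference shares the weakness to a lesser degree while it is not restricted to in-IFU cases.

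The binomial figures are illustrations and not estimates of bias in a planned test. They depend on f, on Background rates whose time horizon is not given, and on a 10% reference that the plan does not adopt. The bias is large if few enrolled necks are hostile and vanishes as f approaches 1.

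**What to change.** Leave the population and the aim as they are, and make these changes:

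1. In section 5, delete the claim of confirming fewer complications than complex techniques. Alternatively, label any such comparison descriptive and confounded by anatomy.
2. Limit conclusions to in-IFU patients with mismatched renal arteries.
3. Restrict literature comparison to standard EVAR performed inside IFU.
4. Classify each neck as hostile or favourable by the Background thresholds (length under 15 mm, angle over 60°, diameter over 28 mm). Lengths, diameters and angles are already in the eCRF. State in advance which of the recorded measurements is used for each; for length, the infrarenal L1 and not L3, which adds the inter-renal segment.
5. Report technical success and type-Ia endoleak by class with exact 95% confidence intervals.

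Do not build a blended benchmark from the 94% and 10% rates. The documents do not show that those rates apply to in-IFU hostile necks, or that the cited technical success uses this study's definition, which includes patency of both renal arteries.

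The cost is some wording and one derived variable. The conclusion becomes narrower and the subgroup intervals will be wide. With 0 events the exact upper limit is 1 − 0.025^(1/n), which is 7.1% for n = 50 and 13.7% for a class of 25.

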Surgical procedure

All the procedure were carried out in a standard operating room equipped with a mobile C-Arm, or in a Hybrid theater under local sedation or general anesthesia on the basis of comorbidity and/or surgeon preference. A bilateral percutaneous access was obtained, even if based on the specific case a cut-down and contralateral percutaneous access is possible. Hemostasis was achieved using the Proglide/Prostyle (Abbott Vascular, Abbott Park, IL, USA) if percutaneous access was used. Intraoperative heparin dosing varied by the center. However, generally, heparin was administered to maintain an activated clotting time > 250 seconds, when possible.

Techniques for delivery and deployment of the standard device have been well described by different papers¹⁰⁻¹², but for the “prototype” some attention is required.

Once the device was advanced at the level of the lowest RA the C-Arm has been moved to correct the parallax effect and positioned orthogonally to the origin of the artery. This procedure permits perfectly matching the scallop with the artery takeoff.

A selective angiogram was performed to assure the patency of the lower RA.

After the deployment of the main body proper iliac extensions were delivered to completely exclude the aneurysm as standard practice.

The complete exclusion of the AAA was checked with a final angiography and then all devices were removed. Heparin was antagonized with the appropriate dose of protamine and access was closed.

According to our standard of care, patients are discharged on the second postoperative day on either aspirin or clopidogrel, if not already on one of these medications.

Follow-up

The first clinical evaluation (before surgery) was performed before discharge primarily to check the femoral access. All the patients will be assessed clinically and with a high-quality CTA (from 6th rib to groin) within 3 months from surgery and yearly for 5 years thereafter for a total of seven evaluations. All the visits will be performed by Investigators.

The patients will be followed up via telephone call to strictly adhere to the present scheme.

A telephone number of the Vascular Surgery Unit will be daily available for any patient's clinical issue during the study period. The clinical and radiological follow-up will continue regularly as a standard practice also in case of patients' voluntary withdrawal.

Endpoints

Primary endpoint: Clinical effectiveness measured in terms of technical and clinical success.

Technical success was defined as defined on an intent-to-treat basis and requires the successful introduction and deployment of the device in the absence of surgical conversion or mortality, type I or III endoleaks, or graft limb obstruction. A technical success thus implies the following qualifying details: 1. Successful access to the arterial system using a remote site (ie, the femoral, external iliac, common iliac, or brachiocephalic arteries with or without the use of a temporary or permanent prosthetic conduit to access these arteries); 2. successful deployment of the endoluminal graft with secure proximal and distal fixation; 3. absence of either a type I or III endoleak; 4. patent endoluminal graft without significant twist, kinks, or obstruction (>30% luminal stenosis or a pressure gradient >10 mm Hg) by intraoperative measurements; 5 patency of both renal arteries and at least one hypogastric artery. Primary technical success can include the use of additional modular components, stents, angioplasty, and adjunctive surgical procedures. However, if unplanned endovascular or surgical procedures are necessitated it must be noted.

Clinical success requires the successful deployment of the endovascular device at the intended location without death as a result of aneurysm-related treatment, type I or III endoleak, graft infection or thrombosis, aneurysm expansion (diameter >5 mm, or volume >5%), aneurysm rupture, or conversion to open repair, occlusion of the renal arteries. The clinical success was measured at every follow-up interval. Any additional maneuvers, planned or unplanned, aimed to maintain clinical success must be carefully reported.

Secondary endpoints:

- Evaluation of the intra-operative and peri-operative (within 30 days) adverse events

- Collection of eventual adverse events related to the treatment procedure and eventual post-hoc analysis
- Evaluation of reintervention (time elapsed since index operation, type, and indication);
- Evaluation of potential risk factors (baseline, anatomical features, procedural technique) potentially related to adverse events
- Evaluation of the main procedural and fluoroscopy time, evaluation of the average contrast medium (CM) dose as well as Dose Area Product (DAP) (mGym3).

Adverse events are defined as any systemic or local complication directly related to the procedure. Adverse events that occurred in the first 30-day were considered procedure-related, unless differently demonstrated.

Any surgical, open, or endovascular, procedure aimed to address adverse events was named re-intervention.

The secondary endpoints represent specific technical aspects related to the procedure and the endograft.

Treatment-related adverse events and re-interventions are important to state the safety of the procedure over time and its external reproducibility.

The procedure and fluoroscopy time, as well as the contrast-medium dose, will be used to evaluate the complexity of the procedure, comparing it with the same reported in the literature for standard EVAR.

Timeline

[figure not shown]
Months 1-3 Organization and logistic set-up.

Months 3-15 Subjects enrollment, data collection, treatments, clinical follow-up.

Months 15-18 Conclusion of recruitment, first (3 months) follow-up end for every patient, ad-interim analysis

Month 27-39 2-year follow-up end, mid-term analysis

Month 63-75 Conclusion of the follow-up, analysis of the results and their validation,

statistical analysis, project completion and analysis for further work, dissemination of the results

Gantt chart:

Sample size

No statistical analysis of the sample size was carried out. Considering the number of AAA responding to the inclusion criteria treated in the participating centers and the enrollment period (1 year) a sample size of 50 patients was estimated. This number should be sufficient to evaluate the endpoints reported in the appropriate section.

The estimated number of patients recruited for the present center is 15 patients

Recruitment

All the involved centers represent the third referral level of complex Abdominal Aortic Aneurysms.

For what concerns our center all patients affected by AAA responding criteria for treatment were evaluated at the Vascular Surgery Unit of the Azienda Ospedaliero Universitaria di Modena. Those meeting the inclusion criteria will be singularly recruited.

Taking into account a mean of 120 endovascular procedures on the abdominal aortic and 10 complex procedures with custom-made devices, a safety 12-month recruitment should be considered. The entire Medical staff of the department is informed about the present project and will refer the potential subjects to the Investigators.

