8. MANAGEMENT OF THE DATA

The collected data will be managed into a dedicated electronic case report form (CRF). The CRFs will be stored on a dedicated and validated website. Only the Investigators will have access to the data with a personal password. Only the PI and the first data manager will be able to see all the data, while the other investigators will have permission to manage only the data of the patients enrolled in their center.

To ensure the correct data collection two Investigators will perform the clinical and radiological assessment at each follow-up visit. Before the conclusion of the visit, a double-check will be performed by the Investigators. The CRF will be completed at the time of enrollment and each follow-up visit thereafter. The CRF required data are declared below.

A personal code will be generated at the enrollment. The CRF will be filled anonymously. The following anamnestic data: age, sex, comorbidities (hypertension, cardiopathy, hyperlipidemia, peripheral arterial disease, previous surgery, etc). Procedure planning details were detailed previously. The procedure details: planned and unplanned adjunctive procedure, the adverse events, the skin-to-skin time, the fluoroscopy time and DAP, the type of anesthesia, the dose, and characteristics of CM used. Primary and secondary endpoints will be registered as defined previously.

The following indicators will also be collected: time of recovery from the intervention and the number of an hour passed in the Intensive Care Unit if needed.

In case of the patient's voluntary withdrawal, the CRF will be discontinued. The patient will undergo standard clinical practice follow-up.

In case of device-related adverse-events, a detailed description of the event will be performed to inform the regulatory authority. The clinical follow-up and the CRF proceed as stated.

In case of death, the study personnel will investigate the cause and any eventual relation with the treatment or device will be declared to the regulatory authority and carefully reported on the eCRF.

Statistical methods

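### After day 30 the secondary safety endpoints can omit graft, device or aneurysm events judged not directly procedural, together with the re-interventions for them

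*Combined protocol and SAP*

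**What the plan says.** All places are in the combined protocol and SAP.

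- **Adverse event (section 7, Endpoints):** "Adverse events are defined as any systemic or local complication directly related to the procedure". The device and the aneurysm are not named.
- **Attribution (same place):** "Adverse events that occurred in the first 30-day were considered procedure-related, unless differently demonstrated". No rule is given for later events.
- **Re-intervention (same place):** "Any surgical, open, or endovascular, procedure aimed to address adverse events was named re-intervention".
- **Secondary endpoints (section 7):** one is "Evaluation of the intra-operative and peri-operative (within 30 days) adverse events". Another is "Collection of eventual adverse events related to the treatment procedure and eventual post-hoc analysis". A third covers re-intervention, with its timing, type and indication.
- **Analysis (section 8, Statistical methods):** freedom from adverse events is estimated by Kaplan-Meier with 95% confidence intervals.
- **Other wording:** section 5 (Study aim) says "To confirm this forecast all adverse events will be reported in our CRF and prospectively monitored" and gives endoleaks as an example of a procedure-related event. Section 8 adds a further class: "In case of device-related adverse-events, a detailed description of the event will be performed". The stated purpose of that description is to inform the regulatory authority.

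**The concern.** An adverse event is normally recorded first and attributed afterwards. Here attribution comes first: after day 30, an event not judged directly related to the procedure is not an adverse event at all. A procedure done to treat it is then not a re-intervention either, because re-intervention is defined through the adverse event.

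Section 7 gives adverse events and re-interventions the role of showing safety over time. Section 5 expects complications to be similar to standard EVAR and fewer than with more complex techniques. The closing paragraph of section 4 says that the data should inform a future off-the-shelf device. If late events pass through an unstated attribution filter, the counts will not be comparable with published counts that lack that filter. Causality that was not recorded at the time is also hard to reconstruct after five years.

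**Working it through.** There is no planned figure to reproduce. Section 7 (Sample size) gives 50 patients from feasibility, without a calculation. The check is a reading of definitions, with an illustration of size.

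**Step 1. Where the definition is used.** The longer-term adverse-event endpoint carries the same restriction in its own wording. The re-intervention endpoint inherits it through the definition. The Kaplan-Meier curve uses the defined term. Section 8 says that endpoints are registered as previously defined, so the CRF follows the narrow term.

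**Step 2. Which late events are exposed.** Primary clinical success (section 7) is assessed at every follow-up interval. Apart from death, its failure criteria carry no relatedness test.

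| Late event | Fails clinical success? | Counts as adverse event after day 30? |
|---|---|---|
| Type I or III endoleak | Yes | Yes, on section 5's use of the term |
| Graft infection or thrombosis | Yes | Only if judged directly procedural |
| Expansion beyond the threshold, rupture, conversion | Yes | Only if judged directly procedural |
| Renal artery occlusion | Yes | Only if judged directly procedural |
| Migration without endoleak | Not listed | Only if judged directly procedural |
| Stent fracture | Not listed | Only if judged directly procedural |
| Limb stenosis without thrombosis | Not listed | Only if judged directly procedural |
| Renal stenosis short of occlusion | Not listed | Only if judged directly procedural |

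The last four rows can drop out of both sets of results. Rows two to four stay in the primary endpoint, but they and the procedures done for them can be missing from the adverse-event curve and the re-intervention count.

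**Step 3. Time covered by the presumption.** Section 6 sets a minimum follow-up of 5 years: 5 × 365.25 ≈ 1826 days. The presumption covers 30/1826 = 1.6% of it, which leaves 98.4% without a rule.

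**Step 4. Size.** One omitted patient moves a crude proportion by 1/50 = 2 points. In general, the understatement = (true rate of exposed events) × (share judged not directly procedural). Both factors are assumptions, because the documents give neither.

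| Assumed rate of exposed events | Expected in 50 | Understatement, share 0 | Share one half | Share 1 |
|---|---|---|---|---|
| 2% | 1 | 0 points | 1 point | 2 points |
| 5% | 2.5 | 0 points | 2.5 points | 5 points |
| 10% | 5 | 0 points | 5 points | 10 points |
| 20% | 10 | 0 points | 10 points | 20 points |

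To show the extreme with exact (Clopper-Pearson) 95% intervals: 5 events in 50 give 10.0% (3.3% to 21.8%) if all count, and 0% (0% to 7.1%) if none does. The assumed rate applies only to exposed events, not to all late failures. An omitted event also leaves the freedom-from-event curve unchanged if that patient already had a counted event.

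**The case against.** The strongest reply is that the primary endpoint already catches what matters most. Clinical success fails, without a relatedness test, on type I or III endoleak, graft infection or thrombosis, expansion, rupture, conversion and renal occlusion. Section 5 treats endoleaks and their re-interventions as procedure-related, so the authors use the term more broadly than its definition. Section 7 also requires additional manoeuvres that maintain clinical success to be reported, planned or not. All of this stands, and it confines the gap to secondary endpoints. It does not close it: reporting a manoeuvre is not the same as counting it as a re-intervention.

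Some stronger readings are tempting, but the documents do not support them:

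- **Late device failures in general vanish from the results.** They do not, for the reason just given.
- **The bias can only favour the prototype.** The 30-day presumption can count unrelated early events against it. The one-sided concern applies only after day 30.
- **Implanting surgeons judge their own cases.** The documents do not say who decides relatedness after day 30. Section 8 has two investigators assess each visit with a double-check. Section 9 has a committee investigate adverse events, and describes the auditing as independent. That committee consists of investigators and no independent event adjudication is described, but self-adjudication is an inference.
- **Sections 5, 7 and 8 contradict one another on what is counted.** The promise to report all adverse events can mean all that meet the definition, and the device-related class can be a subset flagged for the authority. The terms are loose and unreconciled, which is less than a clear conflict.

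**Conclusion.** The point holds in a limited form. Followed as written, the definitions allow the secondary adverse-event endpoint, the re-intervention endpoint and the Kaplan-Meier freedom from adverse events to understate late graft-, device- or aneurysm-related events and the procedures for them. This follows from a stated rule, not from missing detail. Primary clinical success is not affected by the relatedness filter, although its own list leaves out the four residual events named above. For a renal scallop device, renal stenosis short of occlusion is the most pertinent of them.

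The size cannot be derived from the documents. It depends on how many exposed events occur and on how strictly the word *directly* is applied. If investigators read the definition as broadly as section 5 does, the understatement is zero. Otherwise it is 2 points per omitted patient, assuming 50 patients and complete follow-up. The change is worth making before data collection, and no sample-size figure depends on it.

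**What to change.** In section 7:

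1. Define re-intervention as any later procedure on the graft, aneurysm, renal arteries or access vessels, whatever the causality judgement.
2. Extend the adverse-event definition to complications related to the procedure, the device or the aneurysm, at any time after the index operation. Record each of the three relations as a separate CRF field.
3. Run the Kaplan-Meier and re-intervention analyses on this set, and report directly procedure-related events as a subset.
4. Use the same terms in section 5, the secondary endpoints and definitions of section 7, and section 8.

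Putting every untoward event of any cause into the Kaplan-Meier curve is not proposed. It would mix in events unrelated to the graft and make the curve say less about the device.

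The cost is revised wording, a few extra CRF fields and a possibly less favourable event rate. No extra patients or visits are needed.
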